Nudging Flu Vaccination by Making it Easy for Patients to Schedule a Flu Shot

Statistical Analysis Plan

NCT05493787

1/3/2023

Scientific Background and Objectives

The CDC recommends a flu vaccination to everyone aged 6+ months, with rare exception; almost anyone can benefit from the vaccine, which can reduce illnesses, missed work, hospitalizations, and death. Past work from the study team focused on encouraging flu shots for patients with upcoming appointments. However, many patients in the health system do not have any appointments during flu season.

Eligible patients without an upcoming appointment were randomized to a passive control group (no message), an active control group (a basic message stating that the patient can get a flu shot at Geisinger) or one of several other messages informed by behavioral science ("ease", "waiting for you", "protect yourself - rare outcomes", or "protect yourself - frequent outcomes"). Patients were randomly assigned to one of two message send dates. Messages were sent via patient portal and included a link redirecting patients to a page where they could self-schedule a flu shot.

Methods

Patients eligible for the study as of late October 2022 were randomized to a send date (11/8/22 or 12/6/22) and to one of the following study arms:

1. Passive control: No message
2. Active control: A message that simply stated that patients can get a flu shot at Geisinger
3. Ease: A message that emphasized the ease of getting a flu shot at Geisinger
4. Waiting for you: A message that stated the patient's flu shot was "waiting" for them at Geisinger
5. Protect yourself (rare outcomes): A message that emphasized the rare, dangerous outcomes of getting the flu (e.g., hospitalization, pneumonia), and stated that the flu shot can offer protection from those outcomes
6. Protect yourself (frequent outcomes): A message that emphasized the outcomes that frequently occur in people with the flu (e.g., fever, chills, missing important events), and stated that the flu shot can offer protection from those outcomes

All messages included a link redirecting patients to a page where they could self-schedule a flu shot.

Prior to the second message send date, we removed from the study patients who were randomized to the second send date but were no longer eligible (e.g., because they already received a flu shot or who had an appointment newly scheduled).

The final sample includes 139,503 patients.

Power Analysis

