The sample size above allows 80% power to detect an increase in flu vaccination rates from 35% to 36.24% with two-tailed alpha = .05 for any comparison between message arms.

Project Status

All intervention messages have been sent. Data have not yet been extracted from the electronic health records by the study team.

Planned Analyses

Primary Outcome: *Flu shot self-scheduling* [Time Frame: Within 4 weeks of the patient's message send date]

Secondary Outcome: *Flu vaccination* [Time Frame: Within 4 weeks of the patient's message send date]

We will run the following analyses for both the primary and secondary outcomes:

Question 1: Do any of the message versions increase flu shot self-scheduling or flu vaccination relative to no message?

Analysis 1: We will test the hypothesis that all messages significantly increase self-scheduling and vaccination relative to no message. For each outcome, we will run an OLS regression including a categorical predictor variable coding for each individual arm, with arm 1 (no message) as the baseline.

Question 2: Are any of the messages that contain nudge language informed by behavioral science (arms 3–6) more effective than a simple reminder message (active control, arm 2)?

Analysis 2: We will test the hypothesis that messages in arms 3–6, which contain additional nudge language informed by behavioral science, are more effective than active control messages. For each outcome, we will run an OLS regression including a categorical predictor variable coding for each individual message arm (arms 2–6), with arm 2 (active control) as the baseline.

Question 3: Are the arms that include nudge language (arms 3–6) differently effective at promoting self-scheduling or vaccination?

Analysis 3: For each outcome, we will run an OLS regression with a categorical variable coding for nudge arm (arms 3–6). Pairwise comparisons between arms will be corrected using Tukey's HSD.

Question 4: Is it more effective to send a flu shot message in November or December?

Analysis 4: We will run an OLS regression including a binary variable coding for whether or not the patient was sent a message (no message - arm 1; message - arms 2–5), another binary variable coding for send date, and their interaction.

Sensitivity Analyses and Robustness Checks

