Recent work suggests that OLS regressions are appropriate in randomized experiments with binary outcome variables such as ours (Gomilla, 2021). However, as a robustness check, we will also run the regressions described above as logistic regressions instead of OLS regressions. We may run additional sensitivity analyses or robustness checks.

Other Pre-specified Outcomes

Other Pre-specified Outcomes listed below include flu outcomes (diagnosis, complications) and COVID-19 vaccination. If there are any differences in these outcomes as a function of study arm, the mechanism would almost certainly be increased flu vaccination. Therefore, we will only run analyses on Other Pre-specified Outcomes for analyses above where there is a significant difference in flu vaccination.

1. High confidence flu diagnosis

Patient received a flu diagnosis via a positive polymerase chain reaction (PCR)/antigen/molecular test (yes/no) during the 2022-23 flu season (from the patient's study start date through April 30, 2023).

[Time Frame: Up to 8 months]

2. "Likely flu" diagnosis

Received a "high confidence flu" diagnosis (with positive PCR/antigen/molecular test) and/or "likely flu" diagnosis (as assessed via International Classification of Disease [ICD] codes or Tamiflu administration or positive PCR/antigen/molecular test) (yes/no) during the 2022-23 flu season (from the patient's study start date through April 30, 2023).

Note that "likely flu" is a superset of the "high confidence flu" diagnoses.

[Time Frame: Up to 8 months]

3. Flu complications

Diagnosed with flu-related complications (yes/no) from the patient's study start date through July 31, 2023.

[Time Frame: Up to 11 months]

4. ER visits

Number of ER visits from the patient's study start date through July 31, 2023.

[Time Frame: Up to 11 months]

5. Hospitalizations

Number of hospitalizations from the patient's study start date through July 31, 2023.

[Time Frame: Up to 11 months]

6. COVID-19 vaccination rates

Received at least one COVID-19 vaccination (yes/no) during the 2022-23 flu season (from the patient's study start date through April 30, 2023).

[Time Frame: Up to 8 months]

Additional Exploratory Analyses

1. Difference in message version effectiveness by send date

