The group of patients included in our November message send may differ meaningfully than patients included in our December message send: the group in December had relatively more time to get vaccinated before receiving our messages, but still did not get vaccinated. Therefore, it is possible that which particular message is most effective varies as a function of send date.

To explore this possibility, we will run an OLS regression including message arm (with no message coded as baseline), send date (November, December) and their interaction.

2. Age and gender

Messages might be differently effective as a function of age and gender.

To test the relation between flu shots, age and gender, we will run an OLS regression including binned age (18–24, 25–34, 35–44, 45–54, 65+), gender, and their interaction. We will also test for an interaction between age, gender, and study arm.

3. Patients who opened the messages as a function of message type

We will test whether message open rates vary by experimental arm. Open rates may vary because message subjects varied by experimental arm to correspond to message content. We will run an OLS regression including categorical variable coding for arm number (arms 2–6, the arms that were sent messages) with message open within 4 weeks of the message send date as the dependent variable. We will correct for multiple comparisons using Tukey's HSD.

4. Primary and secondary analyses among patients who opened the message

We will run primary and secondary analyses #2–4 above, limiting our sample to patients who opened their messages within 4 weeks of receiving them. In this analysis, we will also remove from the sample patients who scheduled vaccination appointments or were vaccinated before opening their message.

5. Prior year flu shots

We will test whether patients are more or less responsive to our messages as a function of whether they received a flu shot in the 2021–22 flu season. To this end, we will run an OLS regression with a predictor variable coding for experimental arm, a binary predictor coding for whether the patient received a flu shot in the 2021–22 season, and their interaction.

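### Analysis 4 lists the message arms as 2–5 instead of 2–6; coded literally, it leaves arm 6 out of the only planned send-date test

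*SAP*

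**What the plan says.** The SAP's Methods section lists six arms: a no-message control and five messages. Arm 6 is one of the messages: "Protect yourself (frequent outcomes): A message that emphasized the outcomes that frequently occur in people with the flu".

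Under Planned Analyses, Question 4 asks "Is it more effective to send a flu shot message in November or December". Analysis 4 answers it with an OLS regression on a message indicator, a send-date indicator and their interaction, for both the primary and the secondary outcome. The message indicator is defined as "whether or not the patient was sent a message (no message - arm 1; message - arms 2–5".

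The SAP lists the message arms in two other places:

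- Analysis 2: "each individual message arm (arms 2–6), with arm 2 (active control) as the baseline".
- Additional Exploratory Analyses, item 3: "arm number (arms 2–6, the arms that were sent messages".

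The Analysis 4 definition is reused. The robustness section says "we will also run the regressions described above as logistic regressions instead of OLS regressions". Exploratory analysis 4 repeats analyses 2–4 among patients who opened their message. The other pre-specified outcomes are analysed wherever the matching analysis shows a significant difference in vaccination.

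**The concern.** The sentence in Analysis 4 gives two definitions of one variable, and they disagree about arm 6. By its words, arm 6 is coded as messaged. By its arm list, arm 6 is neither control nor message, so its patients drop out of the regression.

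Analysis 4 is the only analysis under Planned Analyses that includes send date. Under the literal coding, the planned answer to Question 4 would describe four of the five messages sent, while the text presents it as covering everyone who was sent one. The plan also leaves the choice of reading open. A report that pools arms 2–6 departs from the arm list, and one that pools arms 2–5 departs from the definition beside it. A reader could not tell which was intended before results were seen.

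**Working it through.** **Inputs.** From the SAP: 139,503 patients, six arms, two send dates, two-sided alpha 0.05, 80% power, vaccination rate 35% rising to 36.24%. Not given and therefore assumed: equal arm sizes, the split between dates, the self-scheduling rate, 0/1 coding of the indicators, and open rates.

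**1. The SAP's power figure.** Patients per arm: n = 139,503 / 6 = 23,250.5. With z = 1.960 + 0.842 = 2.802 and p(1 − p) = 0.35 × 0.65 = 0.2275, the detectable difference between two arms is

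2.802 × √(2 × 0.2275 / 23,250.5) = 1.24 percentage points (pp).

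This matches 35% to 36.24%, so six equal arms fit the SAP's own calculation.

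**2. Patients affected.** With arms 2–6, Analysis 4 has 5 × 23,250.5 = 116,252.5 messaged patients. With arms 2–5 it has 4 × 23,250.5 = 93,002. The loss is about 23,250 patients: one sixth of the sample and one fifth of those messaged.

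**3. Precision of the interaction.** With k message arms pooled and a share f of each arm at one date,

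SE = √{ p(1 − p) × [1/(nf) + 1/(n(1 − f))] × (1 + 1/k) }.

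At p = 0.35 and f = 0.5 this gives 0.6853 pp for k = 5 and 0.6995 pp for k = 4. The ratio is √(1.25 / 1.20) = 1.0206, and it depends on neither p nor f. Power for an effect detectable at 80% becomes Φ(2.802 / 1.0206 − 1.960) = 0.784.

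Under 0/1 coding the send-date coefficient is the date difference within arm 1. Its SE is 0.6256 pp under either reading.

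**4. Detectable interaction at 80% power (2.802 × SE).**

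| Rate | Date split | Arms 2–6 | Arms 2–5 |
|---|---|---|---|
| 35% (SAP, vaccination) | 50:50 | 1.92 pp | 1.96 pp |
| 35% | 60:40 | 1.96 pp | 2.00 pp |
| 35% | 70:30 | 2.10 pp | 2.14 pp |
| 1% (assumed, self-scheduling) | 50:50 | 0.40 pp | 0.41 pp |
| 5% (assumed) | 50:50 | 0.88 pp | 0.90 pp |
| 10% (assumed) | 50:50 | 1.21 pp | 1.23 pp |

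**5. Unequal control arm.** If arm 1 holds a share s of patients and the message arms are equal, the SE ratio is √{ [1/s + 1/(0.8(1 − s))] / [1/s + 1/(1 − s)] }. This is 1.012 at s = 0.10, 1.021 at s = 1/6 and 1.031 at s = 0.25.

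**6. Change in what is estimated.** With equal arms, the interaction over arms 2–6 is 0.8 × (mean of arms 2–5) + 0.2 × (arm 6). If arm 6's date effect differs from that mean by d, the two readings differ by 0.2 × d. Both readings agree only if arm 6 behaves like the average of the others.

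**7. Opened-message rerun.** Arm 1 had no message to open, so the only contrast left is November versus December among messaged patients. If arm 6's open rate is r times that of the other arms, the SE ratio is √((4 + r) / 4): 1.095, 1.118 and 1.140 for r = 0.8, 1.0 and 1.2.

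**The case against.** The strongest reply is that the SAP resolves the slip itself. The wording of the indicator, the arm list in Methods, Analysis 2 and exploratory analysis 3 all point to arms 2–6, and an analyst who builds the variable from its description will include arm 6. Even on the literal reading, arm 6 is still compared with no message in Analysis 1, which uses "a categorical predictor variable coding for each individual arm, with arm 1 (no message) as the baseline". It is compared with the active control in Analysis 2 and with the other nudges in Analysis 3. Send date is also modelled with no arm excluded in exploratory analysis 1: "we will run an OLS regression including message arm (with no message coded as baseline), send date (November, December) and their interaction". No conclusion is likely to turn on a 2.1% larger SE.

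Most of this stands. The intended meaning is fairly clear, arm 6 is well covered elsewhere, and the precision loss is slight. The loss of about 12% belongs only to an exploratory contrast in a subset defined after randomisation, so it should carry little weight. The other pre-specified outcomes inherit the definition only if Analysis 4 is significant for vaccination.

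The reply does not remove the contradiction. An arm list is a coding instruction, and it is the part of the sentence most likely to be copied into a program. Exploratory analysis 1 does not replace a planned analysis, and Analyses 1–3 do not include send date.

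**Conclusion.** The concern holds. Analysis 4 is wrong as written: its arm list contradicts its own definition and the SAP's two other lists of the message arms, with no stated reason. It is probably a slip, and the effect is modest. Excluding arm 6 does not bias the comparison of arms 2–5 with arm 1. With six equal arms, an assumption that reproduces the SAP's power figure, the interaction SE rises 2.1% whatever the outcome rate or date split. It rises 1.2% to 3.1% if arm 1 holds 10% to 25% of patients. The substantive cost is scope and clarity: the planned send-date result would leave out one of five messages and one fifth of messaged patients. It should be fixed because the error is definite and the correction is trivial.

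**What to change.** In Analysis 4, change the message arms from 2–5 to 2–6. The SAP, dated 1/3/2023, says outcome data had not yet been extracted. If that is still so, correct the text before extraction; otherwise use a dated amendment. State that the correction also applies to the logistic rerun, the opened-message rerun and any analyses of the other pre-specified outcomes that follow from Analysis 4. If leaving out arm 6 was intended, the SAP should say why and reword the indicator and Question 4 to match.

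Separately, and of minor importance, the age bins in exploratory analysis 2 go from 45–54 straight to 65+. Add a 55–64 category so that those patients, whose share is not stated, are not left unclassified.

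The cost is one digit and one age bin. No new data are needed.

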GENERAL INFORMATION

Nudging flu vaccination by making it easy for patients to schedule a flu shot

[name].
[contact]

September 25, 2022

IRB#: 2022-0500

BACKGROUND AND OBJECTIVES

On average, 8% of the US population gets sick from the flu each flu season (Tokars et al., 2018). Since 2010, the annual disease burden of influenza has included 9-45 million illnesses, 140,000-810,000 hospitalizations, and 12,000-61,000 deaths (CDC, 2020). The CDC recommends a flu vaccination to everyone aged 6+ months, with rare exception; almost anyone can benefit from the vaccine, which can reduce illnesses, missed work, hospitalizations, and death (CDC, 2019). Flu vaccination is especially important during the COVID-19 pandemic, to minimize flu/COVID-19 coinfections and conserve healthcare resources.

Two past Roybal pilots focused on outreach to patients with upcoming appointments (e.g., Milkman et al. 2021). However, many patients in the health system do not have any appointments during flu season. Messaging patients without a scheduled appointment with a way for them to easily self-schedule a flu shot may increase flu shot uptake across the health system.

The present study will test the effectiveness of a patient-facing nudge, encouraging patients without an upcoming appointment to get a flu shot. This study builds on Geisinger and Penn Medicine Roybal-funded pilots evaluating high-risk messages sent to patients with or without an upcoming appointment (Rosenbaum et al., 2021; Shermohammed et al., 2021), and timely notifications encouraging patients to get the flu shot at their upcoming appointment (e.g., Milkman et al. 2021).

Specific Aim

Evaluate via randomized controlled trial the efficacy of sending messages encouraging flu shots to patients with no scheduled appointment during flu season.

PROCEDURES

Research Design

Patients will be randomly assigned to one of up to six study arms. Outcomes during the 2022–2023 flu season will be compared between study arms.

Study Population

1) Primary target population

Inclusion Criteria:

- Included in one or both of the following two base patient lists:
 - Community Medicine Service Line (CMSL)/Marketing patient portal flu outreach list for Fall 2022
 - A list of patients obtained from Geisinger's Phenomics and Clinical Data Core (PACDC; see Data Sources below for more on this list)
- Aged 18 or older as of October 2022

- Has had a Geisinger encounter in the last 2 years as of October 2022

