After we obtain the base sample lists from PACDC and CMSL/Marketing, **Business Intelligence & Advanced Analytics** (BIAA), working with PACDC, will pull a dataset to help us determine who meets our inclusion criteria and aid in NIH demographics reporting. This dataset will include demographic information, including patient birth date, race, ethnicity, and gender and/or sex. Finally, the dataset will include death date to ensure patients are living as of the date the data are extracted.

After the intervention is complete, we will obtain experimental outcome data for all population groups from BIAA & PACDC. This will include data on patient flu vaccination, diagnosis of flu, diagnosis of flu-like symptoms, presence of flu-associated complications, hospital visits, emergency department visits, and COVID-19 vaccination status. This dataset will additionally include patient characteristics that can serve as analysis covariates, such as: patient primary care provider and flu-related behavior and outcomes during previous flu seasons.

We may also request claims data from the Geisinger Health Plan (GHP; e.g., for claims related to flu vaccination, diagnosis, and complications). GHP claims data will be pulled by BIAA or the GHP data team (pending approval from Research Contracts).

STUDY DATA DETAILS

Data Management Procedures and Confidentiality

The complete, identified study data will be accessed only by a Geisinger data broker and by limited Geisinger investigators with appropriate training and a legitimate need to know (i.e., Geisinger Co-Is and PIs), and any appropriately trained Geisinger staff, (e.g., clinicians, data analysts) who have a need to review the data for purposes of their normal Geisinger role.

A limited dataset containing dates of service and ZIP codes may be shared with any non-Geisinger collaborators (e.g., [name] and his team) under a Data Use Agreement (pending approval) in compliance with HIPAA's Privacy Rule and using data security protocols reviewed and approved by the Geisinger Security Office, Privacy Office, and Information Technology department.

All data will be electronic. Datasets with full identifying information will only be stored on Geisinger-managed, password-protected computers of the data brokers for the purpose of linking datasets from different sources.

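### The age bins in exploratory analysis 2 leave out ages 55–64, so patients in that decade have no category in a pre-specified model

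*SAP*

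**What the plan says.** Under Additional Exploratory Analyses, item 2 (Age and gender), the SAP gives this motive: "Messages might be differently effective as a function of age and gender". It then specifies two steps.

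- The first is an OLS regression of flu shots on "binned age (18–24, 25–34, 35–44, 45–54, 65+), gender, and their interaction". This model has no term for study arm.
- The second reads: "We will also test for an interaction between age, gender, and study arm". No age coding is given for this step.

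Eligibility by age is set in the protocol under Study Population: "Aged 18 or older as of October 2022". No upper limit is given. Age can be computed for everyone, because the protocol says under Data Sources: "This dataset will include demographic information, including patient birth date, race, ethnicity, and gender and/or sex". The SAP's Methods section gives the number analysed: "The final sample includes 139,503 patients".

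**The concern.** The five bins do not cover the enrolled age range: a patient aged 55 to 64 falls in none of them. The SAP does not say what happens to such a patient, and the two likely outcomes in software differ.

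- If age is coded as a categorical variable with the five listed levels, ages 55–64 become missing and drop out of the model.
- If a separate indicator is built for each non-reference bin, these patients score zero on all of them and join the reference bin, with no error message.

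At stake is the question that the analysis was written to answer. If the bins carry over to the interaction with arm, the pre-specified test has nothing to say about message effects in this decade. An analyst who finds the gap after seeing outcomes would also have to choose where to put these patients, and that choice would no longer be pre-specified.

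**Working it through.** **1. The plan's nearest figure.** The SAP gives no power or sample size for the age analysis. Its only figure, under Power Analysis, is "80% power to detect an increase in flu vaccination rates from 35% to 36.24% with two-tailed alpha = .05 for any comparison between message arms". Assuming six equal arms, n = 139,503 / 6 = 23,250.5 per arm. With p1 = 0.35, p2 = 0.3624, d = 0.0124 and mean p = 0.3562:

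- n needed = [1.960 × √(2 × 0.3562 × 0.6438) + 0.842 × √(0.35 × 0.65 + 0.3624 × 0.6376)]² / 0.0124² = 23,411 per arm, or 6 × 23,411 = 140,466 in total.
- Power at 23,250.5 per arm = 79.7%.

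The stated 80% is reproduced. It does not involve age, so it neither supports nor weakens this point.

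**2. Coverage of the bins.** Each whole-number age from 18 to 99 was checked against 18–24, 25–34, 35–44, 45–54 and 65+. The ages in no bin are 55, 56, 57, 58, 59, 60, 61, 62, 63 and 64: one unbroken run of ten years, with no overlap elsewhere.

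**3. Is the decade excluded elsewhere?** No exclusion criterion in the protocol is defined by age. The birth-year criterion for the PACDC list (Data Sources) is oddly worded, but its bracketed explanation covers people reaching 18 in 2022 and anyone older, and it does not single out 55–64. Nothing in either document merges the decade into another bin or says that it is left out on purpose.

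**4. Effect on the contrasts.** The age-by-gender model with its interaction is saturated, so each cell mean is estimated only from the patients coded to that cell. Five bins give 5 × 4 / 2 = 10 pairwise contrasts within a gender.

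- *Dropped:* no estimate among the five listed bins changes. What is lost is any estimate for 55–64.
- *Merged into the reference bin:* let the reference bin have n_r patients with mean m_r, and the 55–64 group n_g patients with mean m_g. The reference mean becomes m_r + w(m_g − m_r), where w = n_g / (n_r + n_g). Each contrast against the reference shifts by −w(m_g − m_r). That affects 4 contrasts; the other 10 − 4 = 6 keep their point estimates.

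The same reasoning holds for message effects by age if the model with arm is fully interacted.

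**5. Size.** The documents give no age distribution. The shares below are assumptions. The last two columns use the SAP's 35% base rate, six equal arms, two-sided alpha of 0.05, and no split by gender.

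| Assumed share aged 55–64 | Patients without a bin | Per arm | Detectable difference between two arms at 80% power | Power for 35% vs 36.24% |
|---|---|---|---|---|
| 10% | 0.10 × 139,503 = 13,950 | 2,325 | 3.97 points | 14% |
| 20% | 0.20 × 139,503 = 27,901 | 4,650 | 2.80 points | 24% |

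So even with a bin of its own, this decade would support only a coarse look at differences between arms.

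**The case against.** The strongest reply is that this is a clerical slip in an exploratory item. The closed bins from 25 up are regular ten-year bands, no reason is given for skipping a decade, birth date is held, and an analyst who tabulated the new variable would notice the unbinned patients. Most of that stands, and it limits the weight of the point. It does not remove it, because the text does not settle what was meant. A dropped 55–64 fits the pattern, but 45–54 could also be a slip for 45–64. These give different models, with six bins and five.

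A second reply is that the SAP never says that the interaction with arm uses these bins. That is correct. Reuse is inferred, since no other age coding is offered, and the regression that lists the bins contains no arm term. The conclusion about message effects at 55–64 rests on that inference.

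A third is that merging into the reference bin is hypothetical, because the SAP names neither a reference bin for age nor a coding scheme. That also stands: merging is one possible outcome, not a prediction.

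A reader might infer that every age contrast would be distorted. The plan does not support that: under merging only the four contrasts against the reference bin move, and under dropping none among the listed bins does. A reader might also infer that the trial's main results lose these patients. They do not: Analyses 1–4 under Planned Analyses contain no age term.

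**Conclusion.** The point holds in limited form. As written, the age bins in exploratory analysis 2 leave enrolled patients aged 55–64 without a category, and no other text repairs this. The consequence is confined to that analysis. There would be no estimate for the decade and, if the patients were absorbed into the reference bin, the contrasts against that bin would be distorted.

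The gap itself needs no assumption. Two other parts of the conclusion do: that the interaction with arm uses the same bins, and that the share aged 55–64 is 10–20%, which gives the figure of about 14,000–28,000 patients. The true number cannot be found from the documents.

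The primary and secondary analyses, their power and their conclusions are unaffected. The text should be corrected because it is an operative analysis rule that cannot be applied to all enrolled adults, and because correcting it costs very little.

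**What to change.** In SAP exploratory analysis 2, make the bins cover every age from 18 up. Either:

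- add the missing band, giving 18–24, 25–34, 35–44, 45–54, 55–64 and 65+, which follows the ten-year pattern; or
- correct 45–54 to 45–64, if that was the intent.

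The authors should confirm which was meant. In the same edit, state that these bins also apply to the age-by-gender-by-arm interaction.

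The cost is one or two sentences and no new data. With six arms and gender coded in two levels (an assumption), the three-way interaction has 5 × 4 × 1 = 20 degrees of freedom with five bins and 5 × 5 × 1 = 25 with six. The second option adds none.

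The Project Status section of the SAP says that outcome data had not been extracted at its date. Made before extraction, the change cannot be influenced by results. If extraction has since taken place, record the change as a dated amendment with its reason.

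### SAP exploratory item 4 re-runs Analysis 4 among message openers, where no no-message patients exist and its message and interaction terms cannot be estimated

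*SAP*

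**What the plan says.** Under Additional Exploratory Analyses, item 4, the SAP states: "We will run primary and secondary analyses #2–4 above", and restricts the sample by "limiting our sample to patients who opened their messages within 4 weeks of receiving them". The item also drops anyone who scheduled or was vaccinated before opening.

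Analysis 4 (Planned Analyses, Question 4) asks whether November or December is the better month to send. Its model has a "binary variable coding for whether or not the patient was sent a message", coded "no message - arm 1; message - arms 2–5", plus a binary send-date variable and the interaction of the two.

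The Methods section lists arm 1 as "Passive control: No message". Exploratory item 3 agrees, describing "arms 2–6, the arms that were sent messages". It adds that open rates may differ by arm because the subject lines differed, and it plans to test this.

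On the two send dates, exploratory item 1 warns: "The group of patients included in our November message send may differ meaningfully than patients included in our December message send".

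**The concern.** Analysis 4 needs patients who were sent nothing. The openers-only sample cannot contain any, because a patient who was sent no message cannot open one. Item 4 leaves out Analysis 1, which has arm 1 as its baseline, but keeps Analysis 4, which depends on arm 1 just as much. That looks like an oversight.

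At stake is how the surviving output would be read. Software would drop two terms and return a send-date coefficient. A reader could take it as the answer to Question 4 among engaged patients, although nothing in that sample separates the effect of messaging in a given month from the month itself or from who was still eligible by then.

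A smaller matter concerns Analyses 2 and 3. These can be fitted among openers, but opening happens after randomisation and, on the SAP's own account, may depend on arm. Item 4 does not say that the comparisons are no longer randomised ones.

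**Working it through.** **1. Design of Analysis 4.** Let M = 1 if a message was sent and 0 if not (arm 1), and D = 1 for December and 0 for November. The model is

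E(Y) = b0 + b1·M + b2·D + b3·M·D.

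The distinct rows (1, M, D, M·D) are:

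| Cell | Row | Full sample | Openers |
|---|---|---|---|
| No message, November | (1, 0, 0, 0) | present | absent |
| No message, December | (1, 0, 1, 0) | present | absent |
| Message, November | (1, 1, 0, 0) | present | present |
| Message, December | (1, 1, 1, 1) | present | present |

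- Full sample: four independent rows, rank 4 of 4. All four coefficients can be estimated.
- Openers: two rows, rank 2 of 4. The M column equals the intercept and the M·D column equals the D column. Only b0 + b1 (the November mean) and b2 + b3 (December minus November) can be estimated. The message effect b1 and the interaction b3 cannot be isolated.

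**2. What is lost.** In the full sample the interaction is (message December − message November) − (no message December − no message November). The second bracket carries calendar time and the change in who is still eligible. Among openers only the first bracket is left.

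**3. Arm 6.** Analysis 4 lists arms 2 to 5 as message and does not mention arm 6. If arm 6 is left out, or counted as a message arm, the openers-only rank is still 2. Only coding arm 6 as 0 gives rank 4, and the term would then compare arms 2–5 with arm 6, not message with no message.

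**4. Analyses 2 and 3 among openers.** Analysis 2 (five arms) has rank 5 of 5 and Analysis 3 (four arms) has rank 4 of 4. Both can be fitted; the question is only what they mean.

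**5. Can the bias in Analyses 2 and 3 be sized?** Not from the documents, which give no open rates, opening times or outcome rates among openers. An illustration with assumed inputs shows that the sign can go either way. Suppose no message has any effect, half the patients have a 55% vaccination rate and half 15%, and the reference arm is opened by 60% and 40% of these halves. The rate among its openers is (0.60 × 0.55 + 0.40 × 0.15)/(0.60 + 0.40) = 39.0%.

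- If another subject line raises opening in the second half to 50%: (0.33 + 0.50 × 0.15)/1.10 = 36.8%, a false difference of −2.2 points.
- If it instead raises opening in the first half to 70%: (0.70 × 0.55 + 0.06)/1.10 = 40.5%, a false difference of +1.5 points.
- If opening is the same in both arms: 0.

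The illustration shows that a false difference is possible. It does not estimate its size in this trial.

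**6. The SAP's power figure.** This is the plan's only design figure, and it concerns the full sample. With equal allocation assumed, n = 139,503/6 = 23,250.5 per arm. For 35% versus 36.24%, the null standard error is √(2 × 0.3562 × 0.6438/23,250.5) = 0.00444, and the alternative standard error is the same to that precision. Power = Φ((0.0124 − 1.96 × 0.00444)/0.00444) = 79.7%, which agrees with the stated 80%.

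**The case against.** The best reply is that this is a drafting slip in one exploratory line. The failure shows itself when the model is run, so no false message effect or interaction could be reported. The full-sample Analysis 4, with arm 1 present, still addresses Question 4. All of that stands, and it is why the severity is low. It does not make the line correct: the send-date term would still be produced, and nothing warns that it lacks a comparator. One could suppose that arm 1 was meant to stay in the sample, which would restore the rank, but leaving Analysis 1 out of item 4 points the other way.

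On Analyses 2 and 3, the authors can say that the item is headed exploratory, that the SAP nowhere calls it randomised or confirmatory, and that item 3 discloses and tests the mechanism. They can add that someone who acted before opening cannot have been moved by the message body, so that exclusion has a rationale. These points are fair, and they reduce this part to a suggestion about labelling. Two things remain. Item 4 does not state the consequence of conditioning on opening, and equal open rates in item 3 would not show that the same kinds of patient opened.

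A reader might infer that openers-only differences would be biased by an amount comparable with the SAP's planned "an increase in flu vaccination rates from 35% to 36.24"%. The documents do not support this. Those 1.24 points are the difference detectable with every patient in each arm. By the same formula (35% baseline, 80% power), the detectable difference among openers would be about 2.80, 1.97 or 1.61 points at assumed open rates of 20%, 40% or 60%. The 35% is also a planning rate for vaccination, not a rate among openers and not a self-scheduling rate, which is the primary outcome. The comparison should not be made.

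**Conclusion.** The point holds for Analysis 4 with certainty and without any assumed figure: among openers the message and interaction terms are not estimable (rank 2 of 4), and the remaining send-date contrast does not answer Question 4. It rests only on arm 1 having been sent nothing and on item 4 restricting the sample to openers, both of which the SAP states.

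For Analyses 2 and 3 the supported conclusion is narrower. They are conditioned on an event after randomisation, and then on not having acted before opening, so randomisation does not protect them. Whether they would mislead, by how much and in which direction is unknown. If the same kinds of patient open at the same times in every arm, there is no bias.

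It would be wrong to infer that the trial's main results are compromised. The full-sample primary and secondary analyses do not use opening and are unaffected.

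**What to change.** In exploratory item 4, change the list from Analyses 2–4 to Analyses 2–3. Alternatively, keep a send-date comparison but restate it as a descriptive November-versus-December contrast among openers, and say that Question 4 is answered by the full-sample Analysis 4.

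As a labelling suggestion, add wording such as: *Analyses 2 and 3 among openers are descriptive and non-randomised, because opening follows randomisation and may differ by arm, and because patients who scheduled or were vaccinated before opening are removed. Conclusions about message effectiveness will be drawn from the full-sample analyses.* Showing the openers-only results with and without that removal would be informative but is optional.

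The cost is a few lines of text, plus one extra version of a table if the optional step is taken. No new patients or data are needed. When the SAP was dated (1/3/2023) the study team had not yet extracted outcome data, so the change could have been made then before results were seen. The documents do not give the current status; if results already exist, the same wording can serve as a reporting caveat.
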